### 7.2.1 Adverse Events of Special Interest

Adverse events of special interest include hypophosphatemia, hypersensitivity/anaphylactoid reactions, injection/infusion site reactions, and cardiovascular events. The search strategy will be identified as follows:

- TEAEs of hypophosphatemia:
  - MedDRA PT Blood phosphorus decrease
  - MedDRA PT Blood phosphorus abnormal
  - MedDRA PT Hypophosphataemia
  - MedDRA PT Hypophosphataemic rickets
  - MedDRA PT Rickets familial hypophosphataemic
- TEAEs indicative of hypersensitivity/anaphylactoid reactions:
  - SMQ Anaphylactic reaction
  - SMQ Angioedema
  - PT Hypersensitivity
- TEAEs of injection/infusion site reactions:
  - MedDRA HLT Infusion site reactions
  - MedDRA HLT Injection site reactions
  - MedDRA HLT Administration site reactions NEC
  - MedDRA PT Infusion related reaction

- Cardiovascular TEAEs:
  - Cardiovascular disorders SOC
  - Vascular disorders SOC

The AEs of special interest will be summarized as below:

- Treatment-emergent AESI by SOC and PT
- Serious treatment-emergent AESI by SOC, PT
- Serious or severe treatment-emergent AESI by SOC and PT

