**Table 1. Mean Change from Screening in Hemoglobin, Ferritin, and TSAT (Safety Population) in 1VIT13036**

Parameter	Cohort 1 (N=16)	Cohort 2 (N=19)
Hemoglobin, g/dL		
Screening mean (SD)		
Mean change at Day 35 (SD)	9.2 (1.20) 1.9 (1.38)	9.5 (0.81) 2.8 (1.15)
Ferritin, ng/mL		
Screening mean (SD)		
Mean change at Day 35 (SD)	8.9 (9.94) 35.1 (98.22)	20.2 (67.37) N=18 52.4 (31.70)
TSAT, %		
Screening mean (SD)		
Mean change at Day 35 (SD)	7.5 (4.64) 9.9 (11.54)	3.4 (1.61) N=18 13.5 (6.88)

SD = standard deviation.

Similar percentages of participants in Cohort 1 (56.3%) and Cohort 2 (63.2%) reported at least 1 treatment-emergent adverse event (TEAE). At least 1 drug-related treatment-emergent adverse event was reported by 3 of 16 (18.8%) participants in Cohort 1 and 6 of 19 (31.6%) participants in Cohort 2. Specifically, the only TEAE considered related to study drug that was experienced by >1 participant was urticaria (3 participants in Cohort 2). Other TEAEs considered related to study drug and experienced by 1 participant each included infusion site pruritus, thirst, and hot flush in Cohort 1 and abdominal pain upper, gastroduodenitis, hyperthermia, injection site pain, alanine aminotransferase increased, headache, pruritus, rash, and hypertension in Cohort 2. Two participants in Cohort 1 experienced a serious adverse event. (Table 2)

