### **8.5.3 Adverse Events of Special Interest**

Adverse events (AEs) of special interest include hypersensitivity, hypersensitivity-like reactions, and cardiovascular events. Hypersensitivity and hypersensitivity-like reactions will be identified using standardized MedDRA queries. Cardiovascular events will be identified using the SOCs for cardiac disorders and vascular disorders.

The overviews and summaries that are provided for all TEAEs will also be provided for the AEs of special interest. In addition, the time to onset and time to recovery will be summarized.

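### SAP 7.2.1 names a cardiovascular disorders SOC where protocol 8.5.3 specifies the cardiac disorders SOC, so the special-interest search as written does not select cardiac events

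*SAP*

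**What the plan says.** Protocol 8.5.3 fixes the cardiovascular search in one sentence: "Cardiovascular events will be identified using the SOCs for cardiac disorders and vascular disorders". SAP 7.2.1 turns it into a search list with two lines, "Cardiovascular disorders SOC" and "Vascular disorders SOC". Three tables are then built from the special-interest lists: all such events, serious ones, and serious or severe ones, each by SOC and preferred term.

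For the allergic category, protocol 8.5.3 says "Hypersensitivity and hypersensitivity-like reactions will be identified using standardized MedDRA queries" without naming any query or its scope. SAP 7.2.1 lists three lines: "SMQ Anaphylactic reaction", "SMQ Angioedema" and "PT Hypersensitivity".

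SAP Section 9 lists five major changes from the protocol. None concerns the special-interest definitions or searches. Separately, SAP 7.2 tabulates all treatment-emergent events by SOC, by preferred term and by both, with further tables for severity, relatedness, seriousness, discontinuation and death. SAP 7.2.2 lists the events.

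**The concern.** A search list in a SAP is an operative rule that programmers filter on, so a wrong SOC name is not harmless background text. The protocol's rule needs the cardiac disorders SOC, and the SAP's list does not contain that name. Because the vascular line is correct, a literal run could still produce a populated cardiovascular table. Nothing in that table would tell a reader whether cardiac events were absent or simply not selected.

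At stake is whether the tables meant to gather cardiovascular events contain the cardiac ones. This is an open-label trial of intravenous iron in children, with 36 participants planned per group. At that size a handful of events would shape how the table is read.

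**Working it through.** No sample size, rate or power figure enters this point, and the plan states no figure to reproduce. The check is a comparison of texts.

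**1. Cardiovascular search**

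| Protocol 8.5.3 | SAP 7.2.1 | Same SOC named? |
|---|---|---|
| Cardiac disorders | "Cardiovascular disorders SOC" | No |
| Vascular disorders | "Vascular disorders SOC" | Yes |

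One of the two SOC names matches. The SAP lists vascular disorders separately, so its first line was most likely meant to be the other half of the protocol's pair, cardiac disorders. The text does not say so.

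**2. Is it a declared change?** No. None of the five items in SAP Section 9 covers it. That silence does not settle whether it is a slip or a decision. The same section of the SAP adds hypophosphatemia and injection or infusion site reactions to the protocol's special-interest categories, and Section 9 does not mention those additions either.

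**3. What a literal filter does.** It selects events whose SOC equals one of the two listed names. Events under cardiac disorders meet neither condition, so none is selected by this search. If the programmer reads the line as cardiac disorders, nothing is lost. The loss is therefore all or nothing for that SOC, depending on how the line is read.

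**4. Where the loss would show.** It would affect the three special-interest tables in SAP 7.2.1. The general tables in SAP 7.2 do not use the special-interest lists, so cardiac events remain there under their own SOC and preferred term, and in the SAP 7.2.2 listings.

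**5. Do the general tables replace the special-interest ones?** Only in part. They give the number of participants with any cardiac-disorders event. They do not give the number with any cardiac or vascular event, because a participant with both appears in both SOC rows and the rows cannot be added. The combined serious-or-severe view is also specific to SAP 7.2.1.

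**6. Hypersensitivity search.** Of the SAP's three lines, two are standardized queries and one is a preferred term. The protocol asks for standardized queries in the plural and names none. The SAP's choice is one way to meet that sentence, so there is no mismatch of the kind found in step 1. Neither document gives a narrow, broad or algorithmic scope for the queries.

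**The case against.** The strongest reply is that this is a slip with no practical effect. The SAP heads the list as cardiovascular events, its second SOC matches the protocol, and SAP Section 1 says the SAP is to be read with the protocol. Other slips occur nearby: in SAP 7.2 the last table in the list has SOP where SOC is meant. A careful programmer would probably correct the name, and the general tables hold the events anyway. Most of this stands. It limits the size of the point and makes a slip the likelier explanation. It does not remove the need to act, because the written rule and the protocol differ and a one-word edit makes them agree.

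Two stronger readings are tempting, and the documents do not support them.

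- A reader might infer that the SAP reduces hypersensitivity to one preferred term, or departs from a particular hypersensitivity query required by the protocol. The SAP uses two standardized queries as well as that term, and the protocol names no query. Protocol 8.0 leaves the complete description of methods to the SAP.
- A reader might note the urticaria in the Phase II 15 mg/kg cohort (3 of 19, protocol 3.2), scale it to the 36 FCM participants (3/19 × 36 ≈ 5.7), and infer that about six reactions would be missed. That figure estimates how many cases might occur, not how many the search would lose. Whether urticaria, rash or pruritus falls within the two queries depends on MedDRA content that neither document reproduces, so the loss could be zero. The Phase II cohorts also received single doses, whereas this trial gives two.

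**Conclusion.** The point holds for the cardiovascular search and is small. SAP 7.2.1 does not name the cardiac disorders SOC that protocol 8.5.3 specifies, and no change is declared. Applied literally, the search leaves that SOC out of the special-interest tables. The extent runs from no events to every cardiac-disorders event in those three tables. It cannot be expressed as a number of participants, because the documents give no cardiac event rate.

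The conclusion assumes only that the search is programmed by SOC name. It does not mean that cardiac events would vanish from the safety report, since SAP 7.2 and 7.2.2 still report them. An undercount of hypersensitivity reactions is not shown.

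**What to change.** In SAP 7.2.1, replace "Cardiovascular disorders SOC" with *Cardiac disorders SOC* and leave the vascular line as it is. No entry in SAP Section 9 is needed, because the SAP then follows the protocol. If the sponsor did intend a different grouping, the SAP should define it and Section 9 should record it.

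Optionally, state in the same section whether the anaphylactic reaction and angioedema queries are run narrow, broad or by algorithm, so that the search can be reproduced.

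The cost is one word in the SAP and a check of the programmed search list. The optional line costs one further sentence. Nothing changes in data collection, sample size or the efficacy analyses.

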**Ferrous Sulfate**

## 7.2 Reporting of Adverse Events

Adverse experiences will be elicited by nonspecific questions such as "Have you noticed any problems?" Participants will be encouraged to report adverse events at their onset. Any adverse experience spontaneously reported by, elicited from the participant, or observed by the physician or study staff, shall be recorded on the appropriate Adverse Event page of the eCRF. The investigator will record the date and time of onset, severity, the relationship to study medication, the date and time of resolution (or the fact that the event is still continuing), the action taken, and the outcome of the adverse experience on the Adverse Event page of the eCRF. Whenever possible, the investigator should group together, into a single term, signs and symptoms which constitute a single diagnosis. For example, cough, rhinitis and sneezing might be grouped together as "upper respiratory infection."

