### **8.5.2 Adverse Events**

Adverse events will be coded by system organ class (SOC) and preferred term (PT) using the Medical Dictionary for Regulatory Activities (MedDRA) dictionary.

The number and percent of participants who report TEAE will be summarized for each treatment group. A TEAE is an event with onset date on or after the study drug start date.

Adverse event summaries will exclude preferred terms that describe asymptomatic serum ferritin, TSAT, and reticulocyte values (or changes). This approach is justified by the reporting of these values in efficacy summaries and is consistent with the protocol-defined reporting standards for hemoglobin/hematocrit and low iron indices. For the purposes of this study, non-serious anemia (hemoglobin or hematocrit below the normal range or worsened from baseline) or iron deficiency (iron indices below the normal range or worsened from baseline) will not be considered adverse events. Anemia or iron deficiency will be considered end points if an intervention is required.

The adverse event profile will be characterized with severity (as graded by the National Cancer Institute Common Terminology Criteria for Adverse Events [NCI-CTCAE]) and relationship (unrelated and related) to study drug. Related adverse events will be events that are possibly or probably related to treatment in the investigator's judgment.

Participants who report the same preferred term on multiple occasions will be counted once for the preferred term: under the highest severity when summarized by severity and under the closest relationship to study drug when summarized by relationship. If a participant reports multiple preferred terms for a SOC, the subject will be counted only once for that SOC.

The number and percent of participants who report treatment-emergent serious adverse events will be similarly summarized for each treatment group. The number and percent of participants who report treatment-emergent adverse events resulting in discontinuation of study drug will be similarly summarized for each treatment group.

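### SAP 7.2.1 omits special-interest event summaries that Protocol 8.5.3 requires, specifies no count per event category, and Section 9 does not list the change

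*SAP*

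**What the plan says.** Protocol 8.5.3 sets two rules for AESIs. The first is "The overviews and summaries that are provided for all TEAEs will also be provided for the AEs of special interest". The second is "In addition, the time to onset and time to recovery will be summarized".

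Protocol 8.5.2 shows what the first rule covers. For TEAEs, "The adverse event profile will be characterized with severity" and by "relationship (unrelated and related) to study drug". Serious events are summarised by arm, and "treatment-emergent adverse events resulting in discontinuation of study drug will be similarly summarized for each treatment group".

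SAP 7.2.1 defines four AESI categories: hypophosphatemia, hypersensitivity/anaphylactoid reactions, injection/infusion site reactions and cardiovascular events. It then lists three outputs: "Treatment-emergent AESI by SOC and PT", the same for serious events, and "Serious or severe treatment-emergent AESI by SOC and PT". SAP Section 9 lists five major changes from the protocol. None mentions AESIs.

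**The concern.** Safety is half of the primary objective. FCM is given intravenously twice, one week apart, to children. The Phase II study cited in Protocol 3.2 gave single doses, so it says nothing about reactions to a second dose. For each AESI category a reader of the trial report will want to know how many children were affected, whether the events were judged related, how severe they were, whether treatment stopped, how soon after dosing they began and how long they lasted. The protocol committed to most of this. A programmer who follows the SAP's list of tables will produce only part of it, and nothing in the SAP tells the reader that the scope has narrowed.

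**Working it through.** No figure in the plan needs reproducing here. The check sets the outputs side by side.

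| AESI output | Protocol 8.5.2 and 8.5.3 | SAP 7.2.1 |
|---|---|---|
| All events by SOC and PT | required | planned |
| Serious events | required | planned |
| Overview | required | absent |
| Severity | by CTCAE grade | one combined serious-or-severe table |
| Relatedness | required | absent |
| Discontinuation | required | absent |
| Time to onset | required | absent |
| Time to recovery | required | absent |
| Children with at least one event, per category | not spelled out | not specified |
| Disclosed in SAP Section 9 | – | 0 of 5 items |

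**Category counts.** The hypersensitivity category is built from two SMQs and one PT, and the cardiovascular category from two SOCs. SAP 7.2 counts a child once per PT and once per SOC, with no rule across SOCs. Suppose a category spans two SOC rows showing *a* and *b* children. The number of children with any such event then lies between max(*a*, *b*) and *a* + *b*, and the table does not say where.

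**Cover elsewhere in the SAP.**
- SAP 7.2 tabulates all TEAEs by SOC, PT and grade, and related TEAEs and TEAEs leading to discontinuation or withdrawal by SOC and PT. AESI terms appear there, but they are not grouped by category.
- SAP 7.3 summarises days to a given grade and days to return to normal for serum phosphate. These are laboratory values, in FCM children with a normal baseline only.
- SAP 7.2.2 lists adverse events and SAP 7.1 lists exposure.

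None of these is a timing summary for hypersensitivity, infusion-site or cardiovascular events.

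**Data available.** Protocol 7.2 states "The investigator will record the date and time of onset", and the same for resolution. Protocol 6.3.1 and 6.3.2 require start and stop times for each FCM administration.

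**AESI list.** Protocol 8.5.3 names hypersensitivity, hypersensitivity-like reactions and cardiovascular events. The SAP adds hypophosphatemia and injection/infusion site reactions. Section 9 does not mention this either.

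**Scale, as illustration only.** In Phase II at 15 mg/kg, drug-related urticaria occurred in 3 of 19 children (Protocol 3.2).
- Rate: 3/19 = 15.8%, exact 95% CI 3.4% to 39.6%.
- Applied to 36 FCM children: 36 × 0.158 = 5.7. The interval runs from 36 × 0.034 = 1.2 to 36 × 0.396 = 14.3, so about 1 to 14 children.
- If each of two doses carried the same independent risk (an assumption): 1 − (16/19)² = 29.1%, and 36 × 0.291 = 10.5.

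Whether urticaria counts as an AESI depends on the content of the SMQs, which the documents do not give.

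**The case against.** The best defence is that much of the information survives, and a reader could infer more from the gap than the documents support.

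- *Severity has been dropped.* It has not. The third AESI table is itself a severity cut, and SAP 7.2 gives grade by PT for all TEAEs. Severity is reduced for AESIs as a group.
- *Relatedness and discontinuation appear in no table.* They do, in the SAP 7.2 tables for all TEAEs, which include every AESI preferred term. What is missing is the AESI-level summary.
- *Reactions cannot be tied to an infusion or counted by category.* They can, because onset and infusion times are collected and events are listed. With about 36 FCM children, reading listings is workable if events are few. The accurate statement is that no planned summary does this.
- *The protocol promised timing by infusion.* It did not. Protocol 8.5.3 does not say from which dose onset is measured.
- *The change was concealed.* Section 9 claims only to cover major changes, and the SAP introduction says it is to be read with the protocol. Table shells are not in the documents and may show categories separately.

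These points narrow the concern without removing it. The SAP does not say that the Protocol 8.5.3 outputs will be produced in addition to its own list. The Section 9 threshold is not high either, since its second item only settles a wording difference for one endpoint. Tables of all TEAEs by SOC and PT do not yield a count of children per AESI category, and listings are not the summaries that the protocol specified.

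**Conclusion.** The concern holds as a mismatch between protocol and SAP in planned safety outputs. SAP 7.2.1 omits the AESI overview, the AESI relatedness, full-grade severity and discontinuation summaries, and AESI time to onset and recovery. It specifies no count of children per AESI category. Section 9 records neither this nor the change to the AESI list. Phosphate laboratory timing, the SAP 7.2 tables and the listings give partial cover.

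The conclusion rests on comparing the two texts and not on an event rate. The Phase II figure shows only that such events may be few or many (about 1 to 14 of 36), and the figure of about 10 depends on assumed equal, independent risk at each dose. The primary efficacy analysis is unaffected. The change should be made before database lock, because it concerns outputs that the protocol already specified.

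**What to change.** 1. In SAP 7.2.1, restore the Protocol 8.5.3 outputs by AESI category and arm. Give the number and percent of children with at least one event, overall and by relatedness, CTCAE grade, seriousness and discontinuation, plus time to onset and time to recovery.
2. In SAP Section 9, list the added AESI categories and any AESI summary that the sponsor still chooses to omit, with the reason.
3. As a cheap addition beyond the protocol text, measure onset in the FCM arm from the most recent infusion and show the Day 0 and Day 7 doses separately. SAP 2.3.2 counts study days from the first dose, so a reaction on the day of the second infusion (Day 7) would fall on study day 7 + 1 = 8, and its closeness to that infusion would not show.

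The cost is a few extra safety tables, many with small counts that need cautious reading. No new data collection is needed.

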### **7.2.2 Deaths, Serious and Other Significant Adverse Events**

The AEs, serious AEs, AE leading to study discontinuation of study drug or withdrawal from study, and subjects who died during the study will be listed.

### **7.3 CLINICAL LABORATORY PARAMETERS**

Laboratory assessments include hematology, clinical chemistry, and iron indices:

- Hematology: Hgb, Hct, RBC, WBC, MCV, MCH, MCHC, RDW, platelets, differential count, reticulocyte count and reticulocyte hemoglobin content (CHr)
- Clinical chemistry: sodium, potassium, chloride, BUN, creatinine, albumin, alkaline phosphatase, total bilirubin, GGT, AST, ALT, LDH, calcium, phosphorus, glucose, bicarbonate and magnesium.
- Iron indices: serum iron, serum ferritin, and total iron binding capacity (TIBC), and percentage serum transferrin saturation (TSAT).
- Other: Serum pregnancy test

All laboratory parameters will be presented in conventional units. The actual value and mean change from baseline to each scheduled visit will be summarized using descriptive statistics by treatment for each laboratory test group above. All abnormal laboratory values will be presented in listings.

Time course table for serum phosphate will be constructed for FCM subjects in safety population. Descriptive statistics of days to first value of specified CTC grade and days to return to normal will be summarized. Only the subjects that were under FCM treatment and had a normal serum phosphate baseline value will be included in this table.

The number and percent of subjects with treatment-emergent potentially clinically significant (PCS) laboratory values after baseline will be summarized by visit and by treatment. The denominator is all subjects with normal baseline and at least one post baseline assessment in the

safety population and the numerator is the number of subjects with PCS (i.e., meets Grade 3 or Grade 4 AE scale defined in Division of AIDS (DAIDS) Table for Grading the Severity of Adult and Pediatric Adverse Events, Version 2.1 from March 2017 (Division of AIDS, National Institute of Allergy and Infectious Diseases, National Institutes of Health, US Department of Health and Human Services)) at any post-baseline visit.

Shift from baseline AE grade to maximum post-baseline AE grade, and shift from baseline to the last visit in terms of AE grade will be summarized by treatment, separately.

The AE grade for Chemistries and Hematology are defined in Appendix 1.1. BUN, hematocrit, bands and iron indices do not have adverse event scales available and are not evaluated separately as possible AEs.

